## 11 SAFETY MONITORING

### 11.1 Definitions

**Adverse Event (AE):** An adverse event is any untoward medical occurrence in a patient or clinical investigation subject administered a pharmaceutical product and which does not necessarily have a causal relationship with this treatment. An AE can therefore be any unfavorable and unintended sign (including an abnormal laboratory finding), symptom or disease temporally associated with the use of a medicinal (investigational) product, whether or not considered related to the medicinal (investigational) product. Pre-existing conditions which worsen during a study are to be reported as AEs.

In clinical studies, an AE can include an undesirable medical condition occurring at any time, including screening or wash-out periods, even if no experimental treatment has been administered.

**Treatment Emergent Adverse Events (TEAE):** Treatment emergent adverse events are defined as adverse events which occur during or after the administration of the first dose of the investigational medicinal product (IMP) or if present before the first administration of IMP, worsen on study treatment.

**Adverse Drug Reaction (ADR):** An adverse drug reaction is any untoward and unintended response to a medicinal product related to any dose administered.

**Unexpected Adverse Drug Reaction:** Any adverse drug reaction the nature, severity or outcome of which is not consistent with the applicable product information.

In this study, the reference document to be used to evaluate the unexpectedness of the adverse drug reactions consists in *section 5.7 Possible Adverse Reactions*” of the Investigator's Brochure (most recent version).

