## **11.4 Adverse Event Reporting**

All observed or volunteered adverse events occurring during the study period, at any time from the signature of the informed consent until the final study evaluation, regardless of treatment group or suspected causal relationship to study drug, will be recorded on the adverse event page(s) of the eCRF.

The need to capture this information is **not dependent** upon whether the adverse event is considered to be related to the use of the study drug. Also, adverse events resulting from concurrent illnesses and reactions to concurrent medications must be reported. In order to avoid vague, ambiguous, or colloquial expressions, the AE will be recorded using standard medical terminology rather than the patient's own words.

Each AE should be described in detail in the eCRF: nature of the event (a sign, a symptom or a diagnosis preferably), onset and stop dates, severity, relationship to study drug, seriousness (see below *Section 11.5*), action taken including corrective therapy and outcome.

AEs that are believed to be at least possibly related to study drug should be followed until satisfactory resolution or acceptable stabilization.

For all AEs, the Investigator must pursue and obtain the necessary information both to determine the outcome of the adverse event and to assess whether it meets one of the criteria for classification as a serious adverse event requiring immediate notification to the **PV Department of ICTA PM** (see *Section 11.5*). For all AEs, sufficient information should be obtained by the Investigator to determine the causality of the adverse event (e.g., study drug or other illness).

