7.5.1 Adverse events (AE)

AE term (Investigator term) will be assigned to the lowest level term (LLT), and a preferred term (PT) will be classified by a high level term (HLT), a high level group term (HLGT) and a system organ class (SOC) according to the Medical Dictionary for Regulatory Activities (MedDRA) thesaurus, version 19.1 or higher.

An adverse event will be considered as treatment-emergent (TEAE) if AE onset date is between first infusion of CER-001 and last infusion of CER-001 + 28 days, or if AE occurred before the first infusion of CER-001 but gets worse on study treatment. In case of incomplete date(s), see section 7.1.4.

An overview of the number of patients with at least one AE and the corresponding number of AEs will be presented including:

- Any AE
- Any TEAE
- Any serious TEAE
- Any severe TEAE
- Any TEAE leading to dose reduction of the study medication
- Any TEAE leading to temporary discontinuation of the study medication
- Any TEAE leading to permanent discontinuation of the study medication
- Any TEAE related to the study medication (Related = definite, probable or possible)
- Fatal AE
- Fatal TEAE
- Any coronary event (Coronary event = event for which HLGT = Coronary artery disorders)

All PT with HLGT = Coronary artery disorders will be described in the same way in a separate table.

CER-001-CLIN-009 CER-001

Note: recurring AEs (*i.e.* AEs classified with the same Preferred Term (PT)) for a given patient will be only counted once and only their most severe intensity or most severe relationship to the study medication will be described.

TEAEs will also be tabulated by System Organ Class (SOC) and PT. They will be presented according to seriousness (Serious / Not serious), severity (Mild/Moderate/Severe) and relationship with the study medication (Related / Not related). They will finally be tabulated by SOC and PT according to relationship with the study medication within severity.

The different analyses described above will be summarized overall, on the induction period and on the post-induction period (AEs that occurred during maintenance or extension phase). Assignment of AEs to periods will be performed as follows:

Period	Assignment
Induction	Start date of TEAE < date of infusion at W10
	(if day of AE is missing then impute to first of the month)
Post-induction	Start date of TEAE ≥ date of infusion at W10
	(if day of AE is missing then impute to first of the month)

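### Read literally, the SAP's AE period rule can move events from post-induction into induction, and never the reverse, when a pre-dose AE worsens late or an onset day is missing in the W10 month

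*SAP*

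**What the plan says.** SAP 7.5.1 gives two routes to treatment-emergent status. The first is onset between the first infusion and 28 days after the last. The second is "or if AE occurred before the first infusion of CER-001 but gets worse on study treatment". Protocol 11.1 has the same second route: an event counts "if present before the first administration of IMP, worsen on study treatment".

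The AE analyses are then "summarized overall, on the induction period and on the post-induction period", and post-induction is explained as "AEs that occurred during maintenance or extension phase". The period table has one test. An event is induction when "Start date of TEAE < date of infusion at W10" and post-induction when "Start date of TEAE ≥ date of infusion at W10". Under both rows the table adds "if day of AE is missing then impute to first of the month".

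Three other places bear on this:

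- Protocol 11.4 lists what is recorded for each AE, including "onset and stop dates, severity, relationship to study drug". A date of worsening is not on the list.
- Protocol 11.4 collects AEs from consent, and Protocol 6.1.1 allows up to 16 weeks of screening, so an AE can start before dosing.
- SAP 7.1.4 deals with incomplete AE dates, but only to decide whether the event is treatment-emergent. It does not assign a period.

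**The concern.** The second route to TEAE status depends on when the event got worse, but the period test looks only at when it started. For such an event the start lies before the first infusion, hence before W10, whatever the date of worsening. The missing-day rule leans the same way: in the month of the W10 infusion, day 1 comes before the infusion unless the infusion was itself on the 1st.

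In both cases an event can be counted in induction although it happened, or became treatment-emergent, in maintenance or extension. That conflicts with the SAP's own description of post-induction. An error in one direction can only make induction look worse and the later periods look cleaner.

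**Working it through.** The plan states no figure for this rule, so there is nothing to reproduce. The check applies the rule as written, assuming that the W10 infusion was given and dated.

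**1. Pre-dose AE that worsens (logic only).** Start date < first infusion < W10 infusion, so the induction condition is always met. Illustrative dates: W0 on 5 September 2016 puts W10 on 14 November 2016. An AE that starts on 22 August 2016 and worsens at W40 is booked to induction, because 22 August precedes 14 November. If the worsening comes before W10, the same booking is right. Only worsening on or after W10 gives an error.

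**2. Undated-day event in the W10 month.** Assumption, not in the documents: the W10 day D and the true onset day T are independent and uniform on 1 to 30.

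- Truly post-induction: P(T ≥ D) = (30 × 31 / 2) / 900 = 465/900 = 31/60 = 51.7%.
- Booked to induction by the rule: P(D > 1) = 29/30 = 96.7%.
- Misplaced: P(T ≥ D and D > 1) = 31/60 − 1/30 = 29/60 = 48.3%.
- Misplaced in the other direction: 0. The rule gives post-induction only when D = 1, and then every day of that month is on or after W10.

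The remaining 29/60 are true induction events, correctly booked.

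**3. Range over the W10 day.** For a given D of 2 or more, the misplaced share is (30 − D + 1)/30:

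| W10 falls on day | Misplaced share |
|---|---|
| 1 | 0% |
| 2 | 29/30 = 97% |
| 15 | 16/30 = 53% |
| 30 | 1/30 = 3% |

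**4. Real calendar.** Crossing every possible W10 date in 2016–2017 with every day of the same month gives 96.7% booked to induction, 51.6% truly post-induction and 48.4% misplaced. This agrees with step 2.

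**5. Other months.** A month before the W10 month lies wholly before W10, and its day 1 gives induction. A month after it lies wholly after W10, and its day 1 gives post-induction. Both are correct.

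**6. Share of all undated-day events.** If these were spread evenly over about 12 months (W0 to W52), the W10 month would hold 1/12 of them. The misplaced share would be 0.483/12 = 4.0%.

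**7. Effect on a table cell.** Thirty patients randomised 2:1 are about 20 and 10 per arm. One patient is 1/20 = 5 points or 1/10 = 10 points, but only where that patient has no other event counted in the same cell.

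**The case against.** The best defence concerns the wording. The TEAE definition in SAP 7.5.1 speaks of AE onset, while the period table speaks of the start of the TEAE. For an event that becomes treatment-emergent only by worsening, that could mean the day it became a TEAE. Protocol 11.1 also requires worsening of pre-existing conditions to be reported as AEs. A condition held as medical history that flares on treatment would then have its own AE record and onset date, and the rule would place it correctly. This part stands: the first problem is confined to AEs already on record before dosing, and only if no new record is opened at the worsening. Neither document says which convention applies, and onset is the only start date that the protocol collects.

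Nor do the documents show that such events will occur. The Visit 1 list in Protocol 8.1 has no AE item and the AE row in Appendix A starts at V2, although collection from consent leaves room for them.

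The consequence is also limited. The tables are descriptive and the rule is prespecified and identical in both arms. The safety objectives are framed at 24 and 48 weeks, not as a contrast of induction with post-induction. Individual listings (SAP 7.7) let a reader check placement. AE checks at every infusion visit (Protocol 8.3) should keep missing days rare. All of this bears on size. None of it makes the booking right where the rule goes wrong, and listings do not correct the tables.

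**Conclusion.** The rule is wrong as written, but the point is minor. Undated-day events in the W10 month are misplaced about 48% of the time under uniform dates (3% to 97% as the W10 day moves from 30 to 2, and none if it is the 1st), always towards induction. Late-worsening pre-dose AEs are also booked to induction, on the condition that no new record is opened at the worsening. Only the by-period AE tables are affected. The documents give no count of such events, and in a trial of 30 patients it is probably small.

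A reader might infer more than this, without support:

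- *That every worsened pre-dose AE is misplaced.* This depends on an eCRF convention that is not shown, and worsening before W10 is booked correctly.
- *That half of all undated-day events are misplaced.* The 48% belongs to one calendar month; with an even spread over a year the figure is about 4%.
- *That most late-worsening events, say 38/48 = 79%, fall after W10.* This assumes that worsening is equally likely at any time from W0 to W48, and nothing in the documents supports it.
- *That each misplaced patient shifts a cell by 5 or 10 points.* SAP 7.5.1 counts a recurring preferred term once per patient, and another event in the same cell absorbs the shift.
- *That the tables distort a planned comparison of weekly with two-weekly dosing.* The SAP does not state that purpose.

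**What to change.** Amend the period table in SAP 7.5.1 before unblinding:

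1. For a TEAE that qualifies by worsening, replace the start date with the date of worsening. This is the onset date of the new record if one is opened, and otherwise the visit at which the worsening was first recorded.
2. For a missing day, keep the first of the month where the month alone decides the period. Where the month contains the W10 infusion, assign by the visit of first report. Events reported up to and including a pre-infusion check at the W10 visit go to induction, and later reports go to post-induction.

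The second rule has to name the pre-infusion check, because Protocol 8.3 asks for an AE check at each visit without placing it before or after the infusion. Without that detail, an event that began between W8 and W10 and was reported at W10 could be moved wrongly into post-induction.

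The sponsor should confirm that the eCRF holds the visit of first report, and say whether a worsened AE gets a new record. If it does, one sentence saying so settles the first problem; the missing-day rule still needs its change.

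The cost is a few lines of SAP text and programming, provided that the visit is stored. The downside is precision: placement by visit is good only to the one- or two-week interval between visits.

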## **10.2 Interruption or Discontinuation of Study Medication**

Patients may be interrupted or discontinued from study medication if any of the following occur:

1. Any drug-related adverse event or other reason which, in the Investigator's opinion, will jeopardize the patient's participation in the trial or the interpretation of trial data (e.g., severe inter-current illness requiring additional care measures or preventing further dosing)
2. Significant tolerability issues

At the time of study medication interruption, the study site will document in the eCRF the reason for drug discontinuation. The patient should continue to be followed clinically and all attempts should be made to re-institute study medication within 21 days of the study drug interruption if not otherwise contraindicated. Study medication may be re-instituted at the initial dose level, or by using a dose reduction scheme as outlined in the following section.

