6.1 Analysis populations of patients

The statistical analysis will be based on the three populations defined below. To be part of a population, patients should have signed informed consent and fullfill all inclusion / exclusion criteria. Some criteria have been added after the start of the study. Hence patients included before will be considered as compliant to these criteria via a Not Applicable (NA) status.

Safety population

The safety population will comprise all randomized patients who received at least one dose of study medication.

Safety analysis will be performed on the safety population according to the actual treatment received.

Modified Intent-To-Treat (mITT) population

The mITT population will comprise all randomized patients for whom at least one of the following conditions is satisfied:

- 3T-MRI assessment available at baseline (W0) and at least one post-baseline 3T-MRI assessment available
- 18FDG-PET/CT assessment available at baseline (W0) and at least one post-baseline 18FDG-PET/CT assessment available

Per Protocol (PP) population

The PP population will comprise all patients of the mITT population without any major protocol deviations (*Cf.* section 6.3).

Defining study populations and excluding patients from the analysis will be a joint decision taken by Sponsor and ICTA PM' representatives (Statistician and Project Leader). Patients to be excluded and

CER-001-CLIN-009 CER-001

reasons for their exclusion will be discussed during data review meetings, before database lock and unblinding.

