7.1 General principles

7.1.1 Software

All statistical analyses will be performed using Statistical Analysis System (SAS®) release 9.4. All computer programs will be developed and validated according to ICTA PM (CRO) standard operating procedures (SOP).

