7.1.4 Management of missing or incomplete data

Previous and concomitant medications

For the purposes of determining whether a medication was taken during the conduct of the study, any missing or partial start or stop dates for which a definitive determination cannot be made will result in that medication will be assumed to be concomitant, to be conservative.

Linear Mixed Model

Missing data handling for assessing efficacy endpoints using linear mixed model will be described in section 7.4.1.

Adverse Events (AE)

If part of the date/time of an AE is missing, but the existing parts allow determination of timing of AE onset/end relative to start and stop date of the study drug, then the AE will be classified (treatment-emergent or not treatment-emergent) per review of the existing parts of the date/time field. If timing of the AE onset/end relative to start and stop date of the study medication cannot be made, then the AE will be assumed to be a Treatment-Emergent Adverse Event (TEAE).

Vital signs, physical examination, ECG and laboratory values

For absolute, relative changes and shifts from baseline (W0), in case of missing data for the baseline value, the latter will be replaced by the value obtained at screening visit.

CER-001-CLIN-009 CER-001

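### The SAP splits adverse events into induction and post-induction by the date of the W10 infusion, with no rule for patients who do not receive that infusion

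*SAP*

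**What the plan says.** SAP 7.5.1 presents its adverse event summaries three ways: overall, for induction and for post-induction. A two-row table assigns events to periods. The induction row reads "Start date of TEAE < date of infusion at W10" and the post-induction row reads "Start date of TEAE ≥ date of infusion at W10". The only imputation given there is for a missing day in the adverse event date. Just above the table, the SAP explains in words what it means by "the post-induction period (AEs that occurred during maintenance or extension phase".

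The tables use the safety population, defined in SAP 6.1: "The safety population will comprise all randomized patients who received at least one dose of study medication". An event is treatment-emergent if it starts "between first infusion of CER-001 and last infusion of CER-001 + 28 days", or if it was present earlier and worsens on treatment.

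SAP 7.1.4 has one fallback for adverse event timing. It begins "If timing of the AE onset/end relative to start and stop date of the study medication cannot be made" and then counts the event as treatment-emergent. It does not deal with an infusion that was not given.

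The protocol expects patients to stop or interrupt treatment. Section 8.7 sets out what to do when study drug is stopped before week 24. Section 10.2 says that after an interruption "all attempts should be made to re-institute study medication within 21 days of the study drug interruption". SAP 7.3.2 lists a reason for an infusion that was not administered. On software, SAP 7.1.1 states: "All statistical analyses will be performed using Statistical Analysis System (SAS®) release 9.4".

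**The concern.** Both rows of the table need a date that exists only if the W10 infusion was given. One dose is enough to enter the safety population, and TEAEs are counted for 28 days after the last infusion. So a patient who stops during induction contributes events to these tables but has no boundary date to sort them by.

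These are patients whose events the induction table should hold. Anyone who stops permanently during induction lacks a W10 date, so the induction row for TEAEs leading to permanent discontinuation is the one most exposed. A reaction to the first infusion that ended treatment could be shown as post-induction, or not appear in either period. With about 20 patients on CER-001 and 10 on placebo, one misplaced patient moves a by-period percentage by about 5 points (1/20) or 10 points (1/10).

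**Working it through.** **Does the written rule work without a W10 date?** Count days from the first infusion, so that W8 is day 56, W10 is day 70 and W12 is day 84. Apply the two rows as written to events starting on days 5, 15, 25 and 75. The SAP gives no code for this step, so two ways of handling a missing date are shown. Both are assumptions about programming; the documents name SAS 9.4 but do not describe how it compares missing values.

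| W10 infusion date | Days 5, 15, 25 | Day 75 |
|---|---|---|
| Present (day 70) | induction | post-induction |
| Missing, ranked below every date | post-induction | post-induction |
| Missing, comparison undefined | neither period | neither period |

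In the second line, onset < missing is false and onset ≥ missing is true, so every event goes to post-induction. In the third line neither condition is met. Neither line agrees with the SAP's wording, under which a day-5 event cannot belong to maintenance or extension.

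**Who lacks the date?** Two groups: patients who stop before W10, and patients who miss the W10 infusion itself and resume later. The second is possible because the 21-day restart target in Protocol 10.2, counted from the first withheld dose, is longer than the 14-day maintenance interval.

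**How many?** The plan's own allowance (Protocol 12.4, SAP section 3) is 24 completers, 20% discontinuation and 30 randomized. It reproduces: 24 / (1 − 0.20) = 30, and 0.20 × 30 = 6 discontinuations. The documents do not give their timing, so these are assumed spreads:

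- Evenly over 48 weeks: 6 × 10/48 = 1.25 patients before W10. With a constant hazard, 30 × (1 − 0.8^(10/48)) = 30 × 0.0454 = 1.36. That is about 1.3 of 30. If patients are independent, the chance of at least one is 1 − (1 − 0.0417)^30 = 72%, or 75% with the constant hazard.
- Evenly over 24 weeks: 6 × 10/24 = 2.5, or 30 × (1 − 0.8^(10/24)) = 2.66 with a constant hazard.
- All before W10: 6, the ceiling within the 20% allowance.

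Patients who miss only the W10 infusion add to each figure; the documents give no basis for counting them.

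**Does the correction work?** Let the boundary be the first maintenance infusion given, with induction as the period if there is none:

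- W10 given on day 70: days 5, 15 and 25 are induction and day 75 is post-induction, as now.
- W10 missed, W12 given on day 84: days 5 to 75 are induction, and onsets from day 84 are post-induction.
- Stopped after W8 (day 56): TEAEs count to day 56 + 28 = 84, and all are induction.

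**The case against.** The intent can be read from the SAP. Its sentence on maintenance or extension would lead a careful programmer to put these events in induction. SAP 7.1.9 provides for the statistician's review of code, logs and outputs and for external review of the tables, and SAP 12.2 requires sponsor-approved dry runs before database lock. A first-infusion reaction shown as post-induction might be caught there. The split serves no stated objective, since the safety objectives are set at 24, 48 and 72 weeks, and the safety output is descriptive. SAP 7.5.1 also lists individually the deaths, other serious events and events leading to dose reduction or discontinuation, with timing relative to the last dose and the number of infusions received.

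All of this stands and limits the consequence. It does not supply the rule. The operative table contradicts the sentence above it for these patients, and SAP 7.1.9 plans double programming only for the primary endpoint.

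Four stronger readings are tempting but not supported:

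- A reader might infer that any dose skipped before W10 causes the problem. It does not: a patient who misses an earlier infusion but receives W10 has the date.
- A reader might infer that several patients will certainly be misplaced. The documents do not time dropout, the even spread over 48 weeks gives little more than one, and the outcome depends on the program.
- A reader might infer a bias between arms, because Protocol section 5 reports more infusion reactions on CER-001. That section also says the reactions were reversible and does not say that they led to stopping. Protocol 3.3.2 reports that no patient in the earlier open-label study in this disease stopped because of an adverse event.
- A reader might suppose that the planned W10 date, first infusion + 70 days, would serve as the boundary. For a patient who stopped after W8, it would put events on days 70 to 84 in post-induction although no maintenance infusion was given.

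**Conclusion.** The point holds as a gap in a stated rule. The period assignment in SAP 7.5.1 cannot be applied to a patient without a W10 infusion and, run literally, gives a result that conflicts with the section's own description of the periods. Whether events would be misplaced in practice depends on the program. The likely extent is small: about 1.3 of 30 patients if the planned 20% discontinuation is spread evenly over 48 weeks and at most 6 within that allowance, plus any who miss only W10. The overall TEAE tables, the individual listings and the efficacy analyses are not touched. The reasons to correct it are that the patients concerned include early stoppers, whose events the induction table exists to show, and that the correction needs no new data.

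**What to change.** In SAP 7.5.1, replace the W10 infusion date in both rows with the date of the first maintenance infusion actually given: W10, or the next infusion given if W10 is missed. Add that all TEAEs of a patient who received no maintenance infusion are assigned to induction.

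The cost is one derived date and one sentence. For a patient who misses W10 and resumes later, the gap counts as induction. This extends what the present rule already does with the interval between W8 and W10. The change does not settle the denominator of the post-induction tables, which is a separate choice.
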